## 5 TREATMENT PLAN

### 5.1 DOSING SCHEMA

**Table 6: Ublituximab/Placebo (Dose Range)**

Cohort	Randomization		Treatment Period	
	Subjects and treatment	Day 1/ infusion time	Day 15/ infusion time	Week 24/ infusion time
1	Placebo (n=2) b	Placebo / 4h	Placebo / 3h	-
	UTX (n=6)	150 mg / 4h	450 mg / 3h	450 mg / 1.5h
2	Placebo (n=2) b	Placebo / 4h	Placebo / 1.5h	-
	UTX (n=6)	150 mg / 4h	450 mg / 1.5h	450 mg / 1h
3	Placebo (n=2) b	Placebo / 4h	Placebo / 1h	-
	UTX (n=6)	150 mg / 4h	450 mg / 1h	600 mg / 1h
4	Placebo (n=2) b	Placebo / 3h	Placebo / 1h	-
	UTX (n=6)	150 mg / 3h	600 mg / 1h	600 mg / 1h
5	Placebo (n=2) b	Placebo / 2h	Placebo / 1h	-
	UTX (n=6)	150 mg / 2h	600 mg / 1h	600 mg / 1h
6	Placebo (n=2) b	Placebo / 1h	Placebo / 1h	-
	UTX (n=6)	150 mg / 1h	600 mg / 1h	600 mg / 1h
Cohort expansiona	Up to 100	To be explored at selected doses pending on the results of the above doses		

a Additional cohorts may be evaluated at doses ranging from 25 mg up to 900 mg to further elucidate the level of B-cell depletion and recovery parameters in subjects with RMS

b Following completion of Day 28, all placebo subjects will enter their respective “a” cohort and receive active treatment as described in Table 7 below. Further, the study evaluation table (section 7) will be restarted for these patients upon the initiation of active treatment with ublituximab

**Table 7: Treatment Schema for Placebo Subjects after Day 28**

Cohort	Subjects	Day 1/ infusion time	Day 15/ infusion time	Week 24/ infusion time
1a	Pbo patients from Cohort 1	150 mg UTX / 4h	450 mg UTX / 3h	450 mg UTX / 1.5h
2a	Pbo patients from Cohort 2	150 mg UTX / 4h	450 mg UTX / 1.5h	450 mg UTX / 1h
3a	Pbo patients from Cohort 3	150 mg UTX / 4h	450 mg UTX / 1h	600 mg UTX / 1h
4a	Pbo patients from Cohort 4	150 mg UTX / 3h	600 mg UTX / 1h	600 mg UTX / 1h
5a	Pbo patients from Cohort 5	150 mg UTX / 2h	600 mg UTX / 1h	600 mg UTX / 1h
6a	Pbo patients from Cohort 6	150 mg UTX / 1h	600 mg UTX / 1h	600 mg UTX / 1h

---

### 5.1.1 DOSE-LIMITING TOXICITY

---

Toxicity will be assessed utilizing the National Cancer Institute Common Terminology Criteria for Adverse Events (NCI CTCAE) v4.0 (<http://evs.nci.nih.gov/ftp1/CTCAE/CTCAE>).

Toxicity will be considered dose-limiting if it occurs during the first 4 weeks of treatment and is considered at least possibly related to ublituximab. Any event defined below, unless the investigator considers the event clearly unrelated to study drug or due to extraneous causes, will be considered a dose-limiting toxicity.

Dose-limiting toxicities will be defined as the following:

- Grade 4 anemia; Grade 4 neutropenia or thrombocytopenia lasting >7 days; Grade  $\geq 3$  febrile neutropenia; and Grade  $\geq 3$  thrombocytopenia with Grade >2 hemorrhage;
- Grade  $\geq 3$  non-hematologic toxicity unresponsive to standard supportive care measure with the exception of:
  - Grade  $\geq 3$  ALT/AST elevation that resolves to  $\leq$  Grade 2 within 7 days;
  - Infusion related reactions (IRR's) Grade  $\geq 3$  related to ublituximab occurring at the 1st infusion, which does not affect continuation to subsequent infusions
- Treatment delay of  $\geq 14$  days due to unresolved toxicity; and
- Non-hematologic toxicity of Grade 2 (at any time during treatment) that, in the judgment of the Investigators, Study Chair, and the Medical Monitor, is dose-limiting.

Adverse events meeting the above definitions but are clearly unrelated to study drug will not be considered DLTs. In rare instances an event may fall within the definition of a DLT as defined above but the event may not be considered a DLT (i.e., not clinically meaningful/significant). If this occurs, a meeting with the Investigator(s), the Medical Monitor, and the Study Chairs, will take place to thoroughly review the event and supporting data, and the reasons for not considering the event a DLT will be clearly documented with supporting rationale. In addition, other events may occur which do not meet the definition of a DLT but are concerning to the Investigator(s), Medical Monitor, and Study Chairs, and may be then considered to be DLTs.

---

### 5.1.2 DETERMINATION OF DOSE-LIMITING TOXICITY

---

The patient population used for determination of DLT will consist of subjects who have met the minimum safety evaluation requirements of the study, and/or who have experienced a DLT. Minimum safety requirements will be met if, during the first 4 weeks of treatment of the study, the patient completes all required safety evaluations, and is observed for at least 4 weeks following the first dose of ublituximab. Subjects who experience a DLT will be considered evaluable regardless of the number of doses received.

Subjects who discontinue treatment early due to disease progression or withdrawal will be asked to have all end-of-treatment safety evaluations performed as described in the protocol. If a patient withdraws from treatment during the first 4 weeks due to any reason other than a DLT, that patient may be replaced.

---

### 5.1.3 STOPPING RULES

---

The DSMB (Study Chairs, Medical Monitor and Sponsor Representative) will be in charge of reviewing safety data after the first 4 weeks of therapy for the last patient in each cohort, and will decide whether or not it is possible to proceed to the next cohort according to the dosing schema described in Section 5.1 These events will be reviewed by the DSMB and potentially other study Investigators at the end of each cohort and routinely thereafter during the course of the study. All other serious and non-serious adverse events will be documented, managed including possible reductions in dose according to investigator discretion, followed until resolution or stabilization, and will also be reviewed by the DSMB at the end of each cohort and routinely thereafter during the course of the study.

The Data Review Group will look at the total safety data in determining whether it is possible to proceed to the next dose cohort and have discretion to apply the following:

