### 4.2 TREATMENT ASSIGNMENT PROCESS

---

A DSMB will be established to safe guard the well-being of the subjects and to advise the Sponsor whether it is appropriate to expand the enrollment to a dosing cohort or to initiate next dosing cohort. The DSMB may also recommend to the Sponsor to terminate the enrollment to a treatment cohort. For example, the DSMB may recommend early termination of enrollment to a dosing cohort that is higher than the optimal treatment cohort after the optimal dosing is determined or a cohort that is considered without meaningful clinical benefit.

Once a subject is qualified, the Site will contact the Sponsor or its designee for cohort assignment (treatment assignment). The Sponsor or its designee will issue the cohort assignment for the subject using the following procedures. If DSMB deems that a cohort is not appropriate (e.g., due to safety), enrollment to that cohort and all higher cohorts will be terminated and all future subjects will be enrolled to the lowest incomplete cohort. Assuming that no safety concern is raised after the DSMB has completed its review based on the safety data from the first two subjects (one placebo and one UTX treatment) in a cohort, the next qualified subject will be enrolled, if applicable. If, however, the new subject is qualified before the DSMB has the opportunity to review the safety data, the new subject will be enrolled to the lowest incomplete cohort. For example, the first two subjects of the study will be enrolled to Cohort 1. If the fourth subject is qualified before the DSMB has the chance to review the safety data from the first two subjects, the subject will be enrolled to Cohort 1.

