#### **Re-consent criteria**

In case of a confirmed diagnosis of MS relapse (as defined in the protocol, Appendix C), **or** in case of an increase in EDSS of 1.0 points or more, sustained for at least 3 months, during the study, the following actions will be taken:

1. The subject will be reminded of the current approved MS medications/treatments and the opportunity to terminate the study and be treated with an approved MS medication.
2. The subject will be requested to re-sign an informed consent form if he/she chooses to continue to participate in the study, in the same treatment assignment.

Subjects enrolled into the study will be closely monitored through the study course by the Sponsor's personnel as well as by an external independent data monitoring committee (DSMB) in order to ensure subjects' welfare.

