## 11 STOPPING RULES

---

An independent DSMB (data safety monitoring board) will be in charge of reviewing safety data. In order to ensure safety and limit toxicity for enrolled subjects, the DSMB will meet (by phone) at least once (prior to subject enrollment (organizational meeting)), after first two subjects have completed infusion (one with placebo and the other with ublituximab) in each cohort during the treatment phase of the study and at end of the completion of the infusion of ublituximab for the eighth subject in each cohort. The independent DSMB may meet more frequently at their discretion depending on the safety and/or efficacy data presented and may stop the study at any time for safety or any other reason after discussing their findings with the Principal Investigator. The independent DSMB will be comprised of at least three MDs, with one being a neurologist and one with experience in the use of anti-CD20 mAb.

---

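### Section 5.1.3 staffs the DSMB from the trial itself and has it decide on the next cohort, against the independent advisory board described elsewhere; Section 4.2 lets enrolment run ahead of the sentinel review

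*Protocol*

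**What the plan says.** All of the following is current text, not the amendment log.

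**Who reviews.** Protocol Section 5.1.3 reads: "The DSMB (Study Chairs, Medical Monitor and Sponsor Representative) will be in charge of reviewing safety data after the first 4 weeks of therapy". The sentence goes on to fix the timing and to hand this body the ruling on escalation: "for the last patient in each cohort, and will decide whether or not it is possible to proceed to the next cohort". Its next paragraph gives the same step to a differently named body: "The Data Review Group will look at the total safety data in determining whether it is possible to proceed to the next dose cohort". That group is not defined in the text provided.

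Section 11 calls the board independent and sets its membership: "The independent DSMB will be comprised of at least three MDs, with one being a neurologist and one with experience" of anti-CD20 antibodies. The re-consent text in the synopsis, Section 5.3 and Section 10.7.3 says subjects are monitored by the Sponsor's personnel "as well as by an external independent data monitoring committee (DSMB"). The synopsis, Section 4.2 and SAP 1.1 give the board an advisory task: "to advise the Sponsor whether it is appropriate to expand the enrollment to a dosing cohort or to initiate next dosing cohort".

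**When enrolment continues.** The synopsis (Study Design) and SAP 1.1 set an order. The first two subjects of a cohort, one on placebo and one on ublituximab, complete 21 days. The DSMB then reviews, and if there is no safety concern the remaining subjects enter. Section 4.2 first says much the same without the 21 days. It then adds that a subject who qualifies before the review goes to the lowest incomplete cohort. Its example places the fourth subject of the study in Cohort 1 while the review of the first two is pending. Section 11 places the sentinel meeting after the first two subjects have completed infusion, without saying which infusion.

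**The concern.** This trial escalates dose and shortens infusion time from cohort to cohort. Two safeguards carry that escalation: an outside board that looks at the data before the next step, and a hold on enrolment until one ublituximab subject and one placebo subject have been observed. Section 5.1.3 undoes the first for anyone who follows it as written, and the exception in Section 4.2 undoes the second. A hold that lapses whenever a subject qualifies early is not a hold.

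The hold matters most where the Day 1 infusion is itself the new step. That is so in Cohort 1, the first exposure in this trial, and in Cohorts 4 to 6, where the Day 1 infusion becomes progressively faster. A subject enrolled early into one of those cohorts receives the new step at the first visit. Two sites or sponsor staff, each following a valid section of the protocol, could expose different numbers of subjects to an unreviewed infusion step under different oversight bodies.

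**Working it through.** The plan gives no figure to reproduce. The check compares the texts and adds a count.

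1. **Can one board satisfy both descriptions?** The number of physicians is not the obstacle, since study chairs and a medical monitor may be MDs. Independence is. A board with a sponsor representative is not external to the Sponsor, and the re-consent text lists the DSMB separately from the Sponsor's personnel. Sections 5.1.3 and 11 therefore describe different boards under one name.

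2. **What is its authority?** In Section 5.1.3 it decides on the next cohort; in the synopsis, Section 4.2 and SAP 1.1 it advises the Sponsor. The undefined Data Review Group adds a second possible decision-maker.

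3. **Does enrolment wait?** Synopsis and SAP 1.1: yes, through 21 days and the review. Section 4.2: only if no subject qualifies in the meantime. Section 11 schedules meetings but does not make enrolment into a cohort wait for them.

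4. **How many could enter early?** Each cohort has 8 subjects, 6 on ublituximab and 2 on placebo (Section 5.1, Table 6). The sentinels are 1 + 1.
   - Remaining: 8 − 2 = 6, made up of 6 − 1 = 5 ublituximab and 2 − 1 = 1 placebo.
   - Entering before the review under the synopsis and SAP 1.1: 0.
   - Entering before the review under Section 4.2: 0 to 6, with no cap stated.

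5. **Does this reach beyond Cohort 1?** The Section 4.2 rule is general; only its example is Cohort 1. Section 5.1.3 opens a cohort after 4 weeks of therapy in the last patient of the previous one. The lowest incomplete cohort will therefore usually be the newly opened, unreviewed one. A lower, already reviewed cohort with places is possible but would be unusual.

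6. **What is the new step in later cohorts?** Section 8.1.3.1 gives the final Day 1 rate for 150 mg in 250 mL, which is 150 / 250 = 0.6 mg/mL.
   - Cohorts 1–3: 100 mL/h × 0.6 = 60 mg/h
   - Cohort 4: 150 mL/h × 0.6 = 90 mg/h
   - Cohort 5: 225 mL/h × 0.6 = 135 mg/h
   - Cohort 6: 450 mL/h × 0.6 = 270 mg/h, which is 450 / 100 = 4.5 times the rate in Cohorts 1–3

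   In Cohorts 2 and 3 the Day 1 infusion is unchanged and the new step is Day 15, so fewer early entrants would reach it before a review.

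7. **Is the count in step 4 a count of exposure?** Not exactly. Placebo subjects start ublituximab on their cohort's regimen after Day 28 (Tables 6 and 7). Since 28 − 21 = 7, a placebo sentinel can be on ublituximab before the review is finished if the review takes more than about 7 days, or if that subject started more than about a week before the active sentinel. This can happen under either rule. Step 4 therefore counts randomised entries.

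**The case against.** The strongest reply is that this is inconsistent wording rather than a chosen design. Section 11 is the section devoted to the DSMB, the re-consent text in three places calls the board external and independent, and Section 11 requires independent meetings in every cohort. On that view escalation without independent advice follows only if Section 5.1.3 is read alone. This is fair, and it sets the category: an internal inconsistency affecting safety oversight. It does not remove the problem, because Section 5.1.3 is where staff would look for the rule on opening the next cohort.

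On the hold, the only worked example is Cohort 1, the slowest regimen, where no lower cohort exists. Extending it to later cohorts is an inference from the sequence in Section 5.1.3. That stands as a caveat; the Section 4.2 sentence itself is not limited to Cohort 1.

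Other protections remain. They include premedication, emergency staff and equipment, investigator control of the infusion rate and a mandatory stop at a second interruption (Sections 5.2, 5.2.1 and 5.2.1.1). They also include the Section 11 meetings and stop authority, SAE reporting within 24 hours (10.8.2), and suspension of accrual after a drug-attributed death (11.1.1).

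Three stronger readings are tempting and not supported:

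- **A trial-wide total.** A reader might multiply 5 ublituximab subjects by six cohorts to get 30 extra exposures. That needs every cohort to fill before its review. No accrual rate or review time is given, Section 11 states a different trigger, and crossover blurs the count.
- **A number of reactions averted.** Section 8.1.1.1 lists infusion-related reactions as common (>20%). However, Section 5.2.1.1 reports them in CLL and NHL, and Section 5.3 says they are more profound in haematologic malignancy. The documents give no rate for RMS by infusion speed.
- **A conflict of interest through DLT rulings.** Section 5.1.1 provides that "a meeting with the Investigator(s), the Medical Monitor, and the Study Chairs, will take place to thoroughly review the event and supporting data" when an event meeting the DLT definition may not be counted as one. Two of those roles also appear in Section 5.1.3. But reasons must be documented, other adverse events also go to the DSMB, and no numerical DLT rule for escalation is stated. The overlap adds little.

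**Conclusion.** Both rules are wrong as written. Section 5.1.3 contradicts Section 11 and the re-consent text on who the DSMB is, and contradicts the synopsis, Section 4.2 and SAP 1.1 on whether it decides or advises. Section 4.2 contradicts the synopsis and SAP 1.1 on whether enrolment waits for the sentinel review.

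The size is 0 to 6 further randomised subjects per cohort entering before review, of whom up to 5 are assigned ublituximab, against 0 under the synopsis and SAP. Where in that range the trial falls depends on accrual and review time. Applying it to cohorts after the first assumes they open in the Section 5.1.3 sequence.

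A reader might infer that escalation in this trial did go ahead, or would go ahead, without independent oversight. The documents do not show that. They show two incompatible instructions, one of which permits it. Confidence is high on the text conflicts; no harm rate can be derived.

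**What to change.** **Section 5.1.3.** Delete the parenthesis on membership. State that the independent DSMB of Section 11 reviews safety data after 4 weeks of therapy in a cohort's last patient and advises the Sponsor on opening the next cohort. Delete the Data Review Group, or define it and say that it does not replace the DSMB.

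**Section 4.2.** Add the 21 days to the sentinel review. Delete the exception and the Cohort 1 example. Write that a subject who qualifies before the review is assigned to a lower cohort that the DSMB has cleared and that has places, or waits. Given sequential opening, waiting will be the usual outcome.

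**Section 11.** Align the sentinel meeting with the 21-day trigger in the synopsis and SAP 1.1. This is a choice between stated triggers and should be recorded as one. SAP 1.1 needs no change.

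**Cost.** Protocol wording, plus an enrolment pause per cohort of about 21 days and review time, which the synopsis and SAP 1.1 already imply. Section 7 allows 28 days for baseline tests and 30 days for MRI before Day 1. A subject tested on the day the pause begins has 28 − 21 = 7 and 30 − 21 = 9 days left for the review and the first dose. Some waiting subjects will therefore need repeat tests or a repeat scan. Qualifying subjects later in the pause limits this.

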### **Suspension of Patient Enrollment:**

In the event of one (1) death attributed to the study drug(s), study accrual will be suspended pending further investigation, and will only be resumed at the recommendation of the DSMB and the Investigators. The DSMB will have discretion to terminate the trial if an additional death occurs that can be attributed to either or both of the study drugs.

## **5.2 AGENT ADMINISTRATION**

---

Treatment will be administered in the MS center. The MS centers must have skilled personnel and adequate equipment to provide emergency treatment should the subject experience anaphylaxis, hypotension or respiratory distress. Subjects will be enrolled into a specified cohort. A single dose of 150 mg of ublituximab on Day 1 with an infusion rate of 4 hours, 450 or 600 mg on Day 15 at different infusion rates (see dosing scheme), and at week 24, a single dose of 450 or 600 mg of ublituximab with different infusion rates will be administered to the respective cohorts. Additionally, 2 subjects in each cohort will be randomized to a placebo group. On day 28, the placebo subjects will begin active treatment with ublituximab in its respective cohort (see dosing scheme). Administration of ublituximab and placebo will be under the direction of the study investigators. Additional dosing cohorts may be explored.

It is required the absolute neutrophil counts and the platelet count should be within normal range before the infusion of ublituximab.

If the liver enzymes (ALT and/or AST) are > 5 times the upper limit of normal (ULN) of the normal range, or if the neutrophil count and platelets counts are below acceptable levels as described, the dose of ublituximab will be held for up to 48 hours until the laboratory values return to within acceptable range. If all labs above do not return to within the acceptable range within 48 hours, the subject will not receive the ublituximab infusion and will be withdrawn from the study. Subjects who are withdrawn will be asked to enter the follow-up evaluation period of the study.

---

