### 3.3 DISCONTINUATION FROM TRIAL TREATMENT

---

Subjects will be discontinued from trial treatment for any of the following reasons:

- Disease progression, defined as 6 month confirmed disability progression ( $\geq 1$  point increase in the EDSS score)
- Irreversible or intolerable toxicity or abnormal laboratory values thought to be related to drug toxicity
- Patient requests to withdraw consent or discontinue treatment
- Pregnancy (see Section 3.3.1)
- Inability of the patient to comply with trial requirements
- Conditions requiring therapeutic intervention not permitted by the protocol
- Inter-current illness (this will be at the investigator's discretion)
- Non-compliance/lost to follow-up
- Discontinuation of the study by the Sponsor

If a patient withdraws from treatment during the first 4 weeks due to any reason other than DLT, that patient will be replaced.

After withdrawal from protocol treatment, subjects must be followed for AEs for 30 calendar days after their last dose of the trial drug. All new AEs occurring during this period must be reported and followed until resolution, unless, in the opinion of the investigator, these values are not likely to improve because of the underlying disease. In this case the investigators must record his or her reasoning for this decision in the subjects' medical records and as a comment on the electronic Case Report Form (eCRF).

All subjects who have CTCAE grade 3 or 4 laboratory abnormalities at the time of withdrawal must be followed until the laboratory values have returned to grade 1 or 2, unless it is, in the opinion of the investigator, not likely that these values are to improve because of the underlying disease. In this case, the investigator must record his or her reasoning for making this decision in the subjects' medical records and as a comment on the eCRF.

---

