## 6 DOSING DELAYS/DOSE MODIFICATION - RECOMMENDATIONS

Subjects should be assessed clinically for toxicity at each visit using the NCI CTCAE v4.0 (<http://evs.nci.nih.gov/ftp1/CTCAE/CTCAE>) grading scale.

Dosing will occur only if a patient's clinical assessment and laboratory test values are acceptable.

Dose modification and or intervention with supportive care recommendations for ublituximab is provided below, however final discretion lies with the treating investigator in regards to more or less aggressive intervention, if the investigational agent needs to be reduced, and actual dose reductions, as well as the number of dose reductions.

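### The protocol contradicts itself at two treatment decisions: laboratory values still abnormal after a 48-hour hold, and a second same-day infusion interruption

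*Protocol*

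**What the plan says.** **Laboratory values.** Protocol section 5.2 sets a condition before dosing: "It is required the absolute neutrophil counts and the platelet count should be within normal range before the infusion of ublituximab". If these counts fall short, or ALT and/or AST exceed 5 times ULN, the dose may be held for up to 48 hours. Without recovery "within 48 hours, the subject will not receive the ublituximab infusion and will be withdrawn from the study". Withdrawn subjects are not simply lost: "Subjects who are withdrawn will be asked to enter the follow-up evaluation period of the study".

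Section 6.2.1.1 covers the same parameters when the toxicity is attributed to ublituximab (scope set in 6.2.1). Grades 1 and 2 need no action, with growth factor to be considered for Grade 2 neutropenia. Grades 3 and 4 are held until a grade threshold is reached or, for platelets and liver enzymes, the subject's previous baseline. Dosing then resumes at the same cohort dose. Section 6.1 also permits delay for toxicity. Section 6 is headed as recommendations and says that "final discretion lies with the treating investigator in regards to more or less aggressive intervention".

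Section 3.3 adds a third wording. Trial treatment ends for "Irreversible or intolerable toxicity or abnormal laboratory values thought to be related to drug toxicity", with no 48-hour limit.

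**Second interruption.** Sections 5.2.1.1, 6.2.1.2.1 and 8.1.3.3 each say that a second interruption for infusion-reaction symptoms means the infusion must stop, with possible completion on a second day. In 8.1.3.3 the bullets just above that sentence, under the heading for a second same-day interruption, allow a restart at no more than half the previous rate after at least 2 hours. Sections 5.2.1.1 and 8.1.3.3 leave the final decision to the treating investigator.

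**The concern.** Whether a subject is dosed, held or withdrawn, and whether an infusion is restarted after a second reaction, should have one answer in a protocol. Here a site can follow one section to the letter and breach another. The immediate stake is subject safety and uniform conduct across sites. The trial also compares small cohorts, each with 6 subjects assigned to ublituximab, on dose and infusion time. Differences between sites in who is withdrawn or whose infusion is completed would be hard to tell apart from differences between regimens.

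**Working it through.** The plan gives no figure to reproduce, so the check sets the passages side by side.

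**(a) Laboratory values at the Day 15 or Week 24 infusion, attributed to ublituximab**

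| Situation | Section 5.2 | Section 6.2.1.1 |
|---|---|---|
| Neutrophils or platelets below normal, Grade 1-2, unchanged at 48 h | No infusion; withdrawn from study | No action |
| Neutrophils or platelets Grade 3-4, improved to Grade 2 within 48 h but not to normal | No infusion; withdrawn from study | Resume |
| Neutrophils or platelets Grade 3-4, recovering only after 48 h | No infusion; withdrawn from study | Hold, then resume |
| ALT/AST above 5 times ULN, not recovered at 48 h | No infusion; withdrawn from study | No withdrawal step at any grade; at Grade 3-4, hold, then resume |

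In each row both instructions cannot be followed. The second row shows that the conflict is about the acceptable range as well as the time limit. The overlap is confined to neutrophils, platelets and ALT/AST. Anemia appears in 6.2.1.1 but not in the 5.2 rule. An abnormality not attributed to ublituximab falls outside the guidelines introduced in 6.2.1.

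**(b) Second same-day interruption for infusion-reaction symptoms**

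| Section | Same-day restart | Stop sentence |
|---|---|---|
| 5.2.1.1 | None after a second interruption | Yes |
| 6.2.1.2.1 | None; wait about 2 hours and monitor | Yes |
| 8.1.3.3 | Permitted, up to 50% of previous rate | Yes, next paragraph |

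Section 8.1.3.3 conflicts with itself and, through its restart bullets, with the other two sections.

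**Minor wording**

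- *Replacement.* Section 3.3 says "If a patient withdraws from treatment during the first 4 weeks due to any reason other than DLT, that patient will be replaced". Section 5.1.2 says "If a patient withdraws from treatment during the first 4 weeks due to any reason other than a DLT, that patient may be replaced".
- *Rate after a first interruption.* Section 5.2.1.1 lets the infusion return to the increments for the treatment dose. Sections 6.2.1.2.1 and 8.1.3.3 limit it to 100 mL/h. For the second infusion in cohort 3, whose planned second step is 400 mL/h, these give different ceilings.
- *First-infusion duration.* Section 5.2, section 8.1.3 and the heading in 8.1.3.1 say 4 hours, the last for all cohorts. Tables 1, 3 and 6 give 3, 2 and 1 h for cohorts 4, 5 and 6. The flow-rate rows in 8.1.3.1 deliver the 250 mL in those shorter times:
  - cohort 4: 10×0.5 + 20×0.5 + 85×1 + 150×1 = 250 mL in 3 h
  - cohort 5: 10×0.5 + 40×0.5 + 225×1 = 250 mL in 2 h
  - cohort 6: 50×0.5 + 450×0.5 = 250 mL in 1 h

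  The rows agree with the cohort tables; the prose and the heading do not.

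**The case against.** The strongest reply is that a hierarchy already exists. Section 5.2 is mandatory and Section 6 is advisory, so a careful site would follow 5.2. Likewise the restart text in 8.1.3.3 is only a permission, so an investigator who does not restart complies with every sentence, and the final decision is the investigator's anyway. It is true that Section 6 is guidance, that its tables cover only toxicity attributed to ublituximab, and that declining to restart breaches nothing. But the protocol states no order of precedence. Section 5.2 has no discretion exception, while Section 6 offers discretion over the same values without pointing back to 5.2. A site that restarts has acted on a sentence in the protocol and against the one that follows it. The restart bullets also cannot be rescued by reading the stop sentence as meaning a further interruption, because 5.2.1.1 and 6.2.1.2.1 apply the same sentence to the second one.

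A reader might infer more than this. The documents do not support the following:

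- *That the DLT definition presupposes longer holds for these laboratory values.* Section 5.1.1 counts a delay of at least 14 "days due to unresolved toxicity", but that covers any toxicity. A delay for anemia, for example, fits both sections, so comparing 14 days with 48 hours measures no conflict.
- *That the 48-hour limit hides DLTs.* A hold starting on Day 15 reaches 14 days on Day 29 (15 + 14), after the 4-week window unless that window is read by onset of the toxicity. Section 5.1.1 also counts Grade 4 neutropenia or thrombocytopenia lasting more than 7 days separately, and lets other concerning events be named as DLTs.
- *That the Week 4 responder rate shifts by a calculable amount.* Withdrawn subjects are asked to enter follow-up, so a Week 4 value may exist. Placebo subjects who cross over are in the SAP's ITT population (SAP 2.2.2), and the SAP does not say whether they are pooled with their original cohort, so even the denominator would be assumed.
- *That planned flow rates above 100 mL/h conflict with the ceiling after a reaction.* A lower ceiling after a reaction is compatible with a higher planned rate. Only the wording between sections differs.

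**Conclusion.** Both contradictions stand in the current protocol text and should be corrected. For ublituximab-attributed neutrophil, platelet or ALT/AST abnormalities, 5.2 and 6.2.1.1 lead to opposite actions on the same subject. For a second same-day interruption, 8.1.3.3 both permits a restart and requires a stop. Investigator discretion reconciles neither.

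No numerical size can be given. Section 8.1.1.1 lists neutropenia, thrombocytopenia and infusion-related reactions as related events in more than 20% of subjects on single-agent ublituximab, so the situations are foreseeable. That list is not an MS rate, however, and it says nothing about values at a planned infusion, recovery within 48 hours or second interruptions. The case rests on safety and consistent conduct, not on a demonstrated effect on the DLT count or the primary endpoint. The replacement, rate and first-infusion wordings are minor and would not carry the point alone.

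**What to change.** 1. Reconcile protocol sections 5.2, 6.1 and 6.2.1.1 into one hold/withdraw rule for neutrophils, platelets and ALT/AST, and check it against the treatment-delay criterion in 5.1.1.
2. Reconcile sections 5.2.1.1, 6.2.1.2.1 and 8.1.3.3 into one second-interruption instruction and one statement of the rate after an interruption.
3. Make 3.3 and 5.1.2 agree on replacement, and make the first-infusion duration in 5.2, 8.1.3 and the 8.1.3.1 heading agree with the cohort tables.

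Which rule applies in each case is for the sponsor's clinicians to decide. The cost is a protocol wording amendment with IRB submission (section 14.1) and a notice to sites. It needs no extra subjects, visits or procedures.
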